## **C. APPROACH**

**Overview.** Given the underwhelming use of MBC in community mental health settings coupled with the demand for performance outcome assessment (Affordable Care Act), this randomized implementation trial aims to compare the effectiveness of a standardized versus tailored approach to implementation of MBC with co-primary outcomes at the clinician (MBC fidelity) and client (depression severity) levels. We will randomize 12 sites of a large community mental health center (Centerstone) to early or later stage standardized or tailored implementation enrolling 150 clinicians and 500 depressed clients in a pragmatic trial (Thorpe et al., 2009). The main clinician level outcome is MBC fidelity, defined as (a) client completion of the PHQ-9, (b) clinician review of scores in the electronic health record, and (c) discussion of scores in session. Phase 1 (months 0-8) will interface the most widely used and validated depressive symptom severity measure (Patient Health Questionnaire-9 item; PHQ-9; [name], 2001) with the electronic health record; this measure is the main client level outcome. Phase 2 (months 8-38) constitutes the active implementation (5 months) and sustainment (10 months) phase. In both conditions, clients will have the option to complete the PHQ-9 on tablets in the waiting room prior to session, which will feed scores to clinicians via the electronic health record. Sites randomized to the standardized condition will begin with a baseline mixed methods needs assessment (for the purposes of putative mediator data collection) and receive the guideline that MBC is to be used in each session with a depressed client. The standardized condition will include manualized training and triweekly group consultation with experts to promote MBC fidelity and optimize its clinical utility. An implementation team (including a site administrator, opinion leader, MBC champion, and research personnel) will convene prior to each triweekly group consultation to review progress and troubleshoot problems. Sites randomized to the tailored condition will also begin with a needs assessment to identify contextual factors that may serve as barriers to the implementation (guided by the *Framework for Dissemination*; [name] et al., 2008; see C7). Training and triweekly group consultation will be tailored to address these barriers (e.g., clinician attitudes toward MBC). The implementation team (same composition as in standardized) will define a site-specific guideline for MBC use (e.g., monthly) and convene prior to each triweekly group consultation to troubleshoot MBC fidelity barriers. At the start of the active implementation across both conditions, depressed clients of participating clinicians will be enrolled to compare the effect of standardized versus tailored MBC implementation on client outcomes. Phase 3 (months 38-48) will characterize MBC fidelity using electronic health record data capture. The evaluation approach is guided by the *Framework for Dissemination* ([name] et al., 2008) and includes a baseline needs assessment, implementation/process evaluation (5 months into implementation), and outcome/impact evaluation (15 months into implementation). This design will allow for a direct test of the assumption that voltage drop in treatment outcomes occurs in the context of adapting the intervention to fit the context (Chambers et al., 2014), while simultaneously exploring the effect of standardized and tailored approaches to MBC implementation.

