**Table 3. Standardized versus Tailored Protocol and Focus**

Contextual Factor	Strategies	Standardized Focus	Tailored Focus
Resources	PHQ-9 in EHR w/ Tablets	Client Completion on Tablets	Client Completion on Tablets
Networks & Linkages	Form Implementation Team	Monitor MBC Fidelity	To Identify Barriers
Policies and Incentives	Guideline	Each Session w/ Client	Determined by Site
Norms & Attitudes	Training	Standardized Protocol	Targets Barriers
Structure & Process	Progress Note Modifications	For Clinician Score Review	For Clinician Score Review
Media & Change Agents	Consultation with Experts	MBC Fidelity	Targets Barriers

consult with clinicians to promote sustainment. Table 3 depicts the protocol and unique focus of the implementation strategies across conditions. A similar blended protocol of implementation strategies led to successful MBC implementation using the PHQ-9 with 90% completion with over 30,000 clients each quarter at Group Health (personal communication, [name], February 11, 2014).

***Standardized Condition.*** The standardized condition includes all aforementioned strategies in the order listed above. The needs assessment will be conducted similar to our pilot study in that it is for data collection purposes only (i.e., no tailoring to identified barriers). The implementation team meetings will focus on monitoring MBC fidelity per the guideline. Depressed clients of clinicians in the standardized condition will be asked to complete the PHQ-9 prior to each session on a tablet in the waiting room

[figure not shown]
(guideline). PHQ-9 data will then be fed to the electronic health record for clinician review. Training will be offered to all enrolled clinicians using standardized material (described in [C9. Pilot Studies](#)). Consultation will focus on incorporating clinician review and discussion of PHQ-9 scores in session and providing tips on targeting lack of progress.

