**Phase 2: Randomized Trial: Implementation & Sustainment.** Implementation will take place across 12 sites in months 8-38 using the dynamic waitlist control design (Brown et al., 2006; C15. Justification and Feasibility). Specifically, matched sites (based on size and urban/rural status) will be randomized to either early or later stage implementation in 4 cohorts (2-4 sites per cohort spaced 5 months apart), with half the sites randomized to the standardized and half to the tailored condition; see Figure 2 for a concise depiction of the implementation timing. The timing of this protocol is based on the published work of Miller et al. (2012) as well as the successful naturalistic MBC implementation at Group Health (personal communication, [name], February 11, 2014). Beginning at month 8, the earliest cohort (2 sites) will engage in the baseline mixed methods needs assessment (Assessment Time 1; AT1). Using purposeful sampling (Palinkas et al., 2013), a subset of clinicians (N=5-8 at each site) representing extreme variation (nominated by clinic directors based on their support for or against MBC implementation) will participate in a 1.5-hour focus group. This sampling approach is critical to gain a wide range of clinician views. Rapid ethnography will then be used to uncover site-specific insights that will guide the content of training and consultation in the tailored condition only (with the aid of mixed method expert [name]; C13b. Data Analysis Plan). During the needs assessment, all enrolled clinicians will complete the battery of baseline measures (see Table 5, Section II), from which the opinion leader (Childers, 1998) and self-nominated MBC champion will be identified and invited to join the implementation team. Across conditions, this team will convene triweekly during the 5-month active implementation period to ensure implementation strategy fidelity (Proctor et al., 2013) and review MBC fidelity. Following the needs assessment, clinicians will participate in a 4-hour MBC training workshop (see C9. Pilot Studies for content) and will begin triweekly consultation. To characterize the differences in implementation team meetings and consultation between conditions, sessions will be audiorecorded and contextual factors logged by graduate research specialist on the MBC Barriers Log (informed by the Framework for Dissemination; [name] et al., 2008; see Appendix for form template). Simultaneously a site team member will log meetings (using the same form) and data triangulated to calibrate site team members and prep for the exit of research personnel. Implementation/Process Evaluations ([name] et al., 2008; AT2) at the clinician level will occur 5 months after the needs assessment at which point the research personnel will be removed. The site implementation teams will be encouraged to continue meeting to promote MBC sustainment and the responsibility to log and address MBC barriers will transfer completely to the site team members. Outcome/Impact Evaluation ([name] et al., 2008; AT3) at the clinician and client level will occur 10 months after the Implementation/Process Evaluation. Focus groups will be held with the implementation team at AT3 to review their experience and the site's progress since the research personnel exited the team. All aforementioned steps will be repeated across the remaining three cohorts.

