In addition, one opinion leader and one self-nominated MBC champion (the opinion leader could also be the MBC champion, but in some cases this will be two different people) will be invited to participate on the implementation team based on the survey results from the needs assessment. The implementation team consists of research team members, site administrator, and 2-4 clinician opinion leader and champion, a client, and office professional. This team will convene for triweekly meetings during the 5-month active implementation phase and they are encouraged to meet without the researchers present during the 10-month follow-up period to facilitate identification of additional barriers (the number of actual meetings and attendance will be documented). Clinicians will be informed that consultation and training sessions will be audio-recorded for research team coding purposes, with the focus on capturing the barriers that emerged and the function of the discussions. Clinicians will be reminded at the beginning of each session not to use client names during consultation sessions to protect client confidentiality. Audio-recorded sessions will be transcribed using the procedures outlined for the focus groups. No clinician study participant identifying information will be retained in the transcripts and only 6-digit anonymous identification numbers will be used. The form found in Appendix B (MBC Barriers Coding Form; Appendix B.1) will be completed by implementation teams during their triweekly meetings; deidentified MBC Barriers Coding Forms will be analyzed for the purposes of research. Additionally, clinicians will have the option to complete the form found in Appendix B (MBC Consultation Form) prior to the triweekly meetings to facilitate consultation, the deidentified MBC Consultation Form form will also be analyzed for the purposes of research. Finally, a battery of surveys will be administered in-person and completed by those on the implementation teams at 5-months and 15-months during an implementation team meeting. These surveys include the Acceptability, Feasibility, Appropriateness for Implementation Teams and Conditions (Lyon, 2011; Appendix A.16-1, A.16-2); [name] Implementation Team Survey (A.19), and Edmondson Team Measure (Edmondson et al, 1999; A.20). These surveys will take about 25 minutes to complete and staff will receive \$15 in compensation per assessment point.

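### After month 5 the plan gives standardized-arm implementation teams two incompatible jobs: monitor fidelity only, or also find and address local barriers

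*Combined protocol and SAP*

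**What the plan says.** **Where the arms are separated.** Table 1 describes tailored content as adapted by the implementation team in response to barriers, and standardized content as manualized in advance. Table 3 assigns the team different tasks: monitoring MBC fidelity in the standardized arm, identifying barriers in the tailored arm. C10, Standardized Condition, repeats this: "The implementation team meetings will focus on monitoring MBC fidelity per the guideline". It adds that the needs assessment there serves data collection, with no tailoring to what it finds. C10, Tailored Implementation Condition, has the team look for remaining barriers to take into consultation.

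**Where barrier work is given to both arms.** C11, Phase 2, describes what happens when research personnel leave at month 5: "the responsibility to log and address MBC barriers will transfer completely to the site team members". No arm is named. Section VII (Study Procedures) describes the team in the clinician, administrator and office-professional parts, each headed as applying to both conditions. Of the teams it says: "they are encouraged to meet without the researchers present during the 10-month follow-up period to facilitate identification of additional barriers". It also says that the MBC Barriers Coding Form "will be completed by implementation teams during their triweekly meetings".

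**What the log is for before month 5.** C11 gives a measurement purpose: "To characterize the differences in implementation team meetings and consultation between conditions, sessions will be audiorecorded and contextual factors logged by graduate research specialist". The site's own log runs alongside: "Simultaneously a site team member will log meetings (using the same form) and data triangulated to calibrate site team members". It also prepares the site for the research team's exit.

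**The concern.** The trial asks whether an implementation matched to local barriers does better than a fixed one. What standardized teams may do with a barrier once they have written it down is therefore part of the comparator's definition, and the plan gives two answers.

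If standardized sites follow C11 and Section VII, they receive some of what the tailored arm is meant to receive, after research staff have left and can no longer hold them to the fidelity focus. H2 expects contextual factors to be leveraged in the tailored arm and to act as barriers in the standardized arm; instructing standardized teams to address barriers works against that. C14 also commits to an interpretation: if the main hypothesis is not supported, the finding would show that customization harms outcomes. That reading is unsafe if the comparator was also told to respond to its local context.

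**Working it through.** The point rests on comparing the text. The arithmetic at the end is illustrative only.

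**1. Team tasks side by side**

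| Period | Standardized team | Tailored team | Source |
|---|---|---|---|
| Months 0-5, focus | Monitor fidelity to the guideline | Identify remaining barriers | Table 3; C10 |
| Months 0-5, form | Complete barriers form triweekly | Same | Section VII |
| Months 5-15, responsibility | Log and address barriers | Same | C11, Phase 2 |
| Months 5-15, purpose of meetings | Find further barriers | Same | Section VII |

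The first row differs by arm; the last two do not.

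**2. Does the C11 sentence really cover both arms?** The same paragraph marks scope where it wants to. It restricts training and consultation content guided by the needs assessment to the tailored arm, and says of the team: "Across conditions, this team will convene triweekly during the 5-month active implementation period". The transfer sentence carries no restriction, and the Section VII headings name both conditions outright. The plain reading is both arms.

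**3. How much of the intervention overlaps?** Table 3 lists six strategies. Two are the same by design (PHQ-9 on tablets, progress-note changes). Four differ: team focus, guideline, training and consultation. The conflict concerns one of those four, team focus. However, C10 and C11 name the site team as the activity sites are encouraged to continue after month 5, so the overlap falls on the component meant to carry sustainment.

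**4. Which analyses use months 5-15?** C13a, Aim 2, takes mediators at the end of the implementation window and uses them to predict PHQ-9 completion in the sustainment window. If standardized teams work on barriers during that window, their month-5 mediator values would tend to predict later completion less well. Table 5 also schedules the fidelity outcome at AT3 (month 15).

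**5. Is separation checked?** The Contamination interview (Section VII, Administrators) is held at the end of active implementation, before the period at issue. C11 and Section VII provide for recordings, barrier forms, and counts of meetings and attendance. C13a and C13b do not say how any of these enter a between-arm separation check or a sensitivity analysis.

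**6. Illustration of size.** C13a states power above 80% (two-sided 0.05) at d = .46 for 150 clinicians. A two-group formula without clustering gives a detectable difference of 2.80 × √(4/150) = 0.457, close to .46. With the stated site ICC of .05 and 150/12 = 12.5 clinicians per site, the design effect is 1 + 11.5 × .05 = 1.575 and the figure becomes 0.457 × √1.575 = 0.574. The plan's value comes from a simulated growth model whose parameters are not all given, so neither result confirms or refutes it. Taking 80% power at d = .46 as stated, let c be the assumed share of the tailoring effect that the standardized arm also obtains:

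power = Φ[(1.96 + 0.84)(1 − c) − 1.96]

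| c (assumed) | d | Power |
|---|---|---|
| 0 | .460 | 80% |
| .10 | .414 | 71% |
| .25 | .345 | 56% |
| .50 | .230 | 29% |

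Nothing in the documents fixes c.

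**The case against.** The strongest case on the other side is that the plan keeps its arms apart where it matters and that the loose wording is minor.

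- **Barrier identification alone does not define tailoring.** Both arms have a needs assessment by design. The tailored arm is defined by content matched to barriers and a site-set guideline. This stands. Aim 3's contrast of adapted with weekly PHQ-9 administration is a guideline difference that barrier logging does not touch.
- **The months 0-5 log is measurement.** This stands. C11 says it is kept to characterize differences between arms.
- **Troubleshooting is compatible with fidelity monitoring.** The C. Approach overview says that the standardized team "will convene prior to each triweekly group consultation to review progress and troubleshoot problems". That can be read as solving problems in following the guideline, so I do not count it as part of the contradiction.
- **Meetings after month 5 are only encouraged.** True, and if few are held the overlap may be small. But the transfer of responsibility in C11 is stated without that qualifier, and addressing a barrier is action, which a measurement purpose does not cover.
- **Equal strategies are deliberate.** C10 matches the protocol across arms to remove time and resource confounds. That justifies equal meetings and equal forms; it does not justify giving both teams the task that Table 3 reserves for one.

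A reader might infer that standardized sites run a barrier-removal programme for all 15 months and that the tested contrast is lost. The documents do not support that: addressing barriers enters only after month 5, and the guideline and the training and consultation content remain distinct.

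**Conclusion.** The contradiction is real and lies in the current text. Tables 1 and 3 and C10 reserve barrier identification and response for tailored teams; C11 and Section VII assign both to all teams in months 5-15. Followed as written, one of the four strategies that distinguish the arms converges during the window that supplies the Aim 2 outcome.

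The likely direction is toward the null, and against H2. That rests on two assumptions: that standardized teams act on the instruction, and that addressing local barriers helps, which is the trial's own hypothesis. The size is unknown. The fall from 80% power to 71%, 56% or 29% should not be read as a prediction: the dilution shares are assumed, .46 is a smallest detectable effect and not an expected one, and the formula dilutes the whole effect although three distinguishing strategies are unaffected. A reader might also infer that a null result would be uninterpretable; the documents support only that it would be harder to interpret unless separation is shown.

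**What to change.** 1. **Reconcile C11 (Phase 2) and the three Section VII descriptions of the team with Tables 1 and 3.** Limit addressing barriers, and meeting to find further ones, to tailored sites. State that standardized teams in months 5-15 review fidelity to the guideline.
2. **Keep the barriers form in both arms through month 15**, and label it in standardized sites as a record for measurement only. Section VII ties the form to the triweekly meetings of the active phase, so its continued use should be written down. Removing it from standardized sites would be a mistake: no research coder is present after month 5, the record needed to detect convergence would be lost, and process measurement would differ by arm.
3. **Add a between-arm separation report to C13**, from data already planned: barrier forms, meeting and attendance counts, recordings and the Contamination interview. Present months 0-5 and 5-15 separately. The interview informs only the first period; the second depends mainly on site-kept forms, meeting counts and the AT3 focus groups with the teams.

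**Cost.** A small wording change for the six standardized sites and a short descriptive analysis. Completing the form may still prompt some standardized teams to act; the separation report should make that visible. C13a is written largely in the past tense and already reports 22.8% of patients without the 12-week interview, so sites may be past month 5. If so, the wording change comes too late for them, and item 3 becomes the main remedy, together with a more cautious reading of a null result than C14 offers.

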## **C12. Participants: Recruitment, Retention, and Data Collection Procedures**

### **C12a. Clinicians**

**Recruitment.** Participants will be recruited across 12 sites (Clinicians:  $N=187$ ; target:  $N=150$ ) (*Letter of Support*: CEO [name]). The number of sites and clinicians has been determined by a simulation-style power analysis to detect a small effect size predicted by previous research (*C13. Data Analysis Plan*). The main sites have been identified, but not enrolled (*Letters of Support* from regional clinic directors). As there are at least 16 sites from which to select (easily accessible from primary site) and at least 250 eligible clinicians across these sites, we are confident that we can obtain the targeted number of both sites and clinicians. Said differently, even if a site administrator enrolls a site, not all clinicians will need to participate, an important factor to avoid any perception of coercion. Given site diversity, the large number of eligible sites will maximize the likelihood that results will generalize to the broader population of community mental health centers. Sites range in size from 12 to 52 clinicians. Within each enrolled site, clinicians will have the option to participate if they (a) are at least 80% full-time equivalent (b) provide individual psychotherapy to (c) adults with depression (d) in English. These inclusion criteria reflect over 95% of clinicians at the eligible sites. Based on our pilot study, we have experienced that even those who are not supportive of MBC have agreed to participate, therefore making it unlikely that self-selection to participate would limit the generalizability of our sample. During Phase 1 (months 5-8; Table 4), clinician enrollment will begin across all sites and site randomization will occur as site level randomization improves project feasibility and reduces contamination confounds. This decision to randomize by site was also influenced by literature indicating the impact of organizational culture and climate on the implementation process (Aarons et al., 2012; Damschroder et al., 2009), which will be assessed at baseline (AT1).

**Data Collection.** See *Table 5: Study Measures, Section II* for concise descriptions of the clinician battery. Each contextual factor of diffusion ([name] et al., 2008) will be assessed via self-report (and qualitatively via focus groups). MBC fidelity is the main clinician level implementation outcome. All clinician measures will be administered across three time points for each cohort with respect to their time since starting implementation: 1) Phase 1: Baseline Needs Assessment (AT1), prior to MBC implementation; 2) Phase 2: Implementation/Process Evaluation (AT2, 5 months in), following the active implementation phase; and, 3) Phase 3: Outcome/Impact Evaluation (AT3, 15 months in) 10 months after the research personnel have exited. Barriers to implementation will be collected for the first month of implementation via the electronic health record.

